
• To evaluate the efficacy of lasmiditan 200 mg, 100 mg, and 50 mg on disability during migraine attacks compared to placebo• To evaluate the efficacy of lasmiditan 200 mg, 100 mg, and 50 mg on health utility compared to placebo• To evaluate the efficacy of lasmiditan 200 mg, 50 mg, and 100 mg on Patient Global Impression of Change (PGI-C) compared to placebo• To evaluate the efficacy of lasmiditan 200 mg, 100 mg, and 50 mg on Health-Related Quality of Life (HRQoL) during an acute migraine attack compared to placebo	
• The proportion of patients in each group with no disability as measured by the disability item, at 2 hours postdose during the attack• Mean change from baseline in utility in each group as measured by the EuroQol 5 dimension 5-level scale (EQ-5D-5L), at 24 hours postdose during the attack• The proportion of patients in each group very much or much better as measured by PGI-C, at 2 and 24 hours postdose during the attack• Mean HRQoL score for domains of social functioning, migraine symptoms, and feelings/concerns, as measured by the 24-hour Migraine Quality of Life Questionnaire (MQoLQ), in each group at 24 hours postdose of study during the attack
--	--

Abbreviations: 24-hour MQoLQ = 24-Hour Migraine Quality of Life Questionnaire; EQ-5D-5L = EuroQol 5-dimension 5-level scale; HRQoL = Health-Related Quality of Life; MBS = the most bothersome symptom as identified by the individual from the associated symptoms of nausea, phonophobia or photophobia; PGI-C = Patient Global Impression of Change; HRQoL = Health-Related Quality of Life; MQoLQ = Migraine Quality of Life Questionnaire.

5. Overall Design

[figure not shown]

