9.1.2. Secondary Efficacy Assessments

Patient Diary

Other efficacy data will also be collected in the eDiary.

At the time points, 0 (pre dose), 0.5, 1, 1.5, 2, 3, 4, 24, and 48 hours, patients will assess the presence or absence (yes or no) of accompanying symptoms: photophobia, phonophobia, nausea, and vomiting. At time 0 (pre dose) patients will select from the accompanying symptoms present (from nausea, phonophobia, or photophobia only) the one that is the most bothersome to them.

Patients will also be asked to record the time of meaningful relief and the time at which they become headache pain free. At 2 and 24 hours after the study drug, patients will be asked to record their Patient Global Impression of Change (PGI-C) using a 7-point scale (very much better, much better, a little better, no change, a little worse, much worse, and very much worse). The eDiary assessments are listed in Appendix 5.

Patients will record details of AEs, concomitant medication use, and any other relevant information in the patient's paper diary and these will be reviewed at the next visit.

Recording Use of Rescue/Recurrence Medication: Refer to Section 7.2.1.1 for details.

Migraine Quality of Life Questionnaire (MQoLQ): The 24-hour Migraine Quality of Life Questionnaire (24-hr MQoLQ) has been specifically developed to measure the Health-Related Quality of Life of patients with migraine within a 24-hour period after having taken migraine medication. The 24-hour MQoLQ is a 15-item, self-administered questionnaire. The items cover 5 domains (work functioning, social functioning, energy and vitality, feelings and concerns, and migraine symptoms) (Hartmaier et al. 1995; Santanello et al. 1995, 1997). Each domain consists of 3 questions answered on a 7-point scale where 1 indicates maximum impairment and 7 indicating no impairment. A domain score is calculated by summing the responses to the 3 questions and the domain score ranges from 3 to 21. The questionnaire will be administered 24 hours after the study drug.

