EuroQol 5-Dimension 5-Level (EQ-5D-5L): EQ-5D-5L questionnaire is a widely used, generic questionnaire that assesses health status (The EuroQol Group 1990; Herdman et al. 2011). This is a patient-rated scale. The questionnaire consists of 2 parts. The first part assesses 5 dimensions (mobility, self-care, usual activities, pain/discomfort, and anxiety/depression) that have 5 possible levels of response (no problems, slight problems, moderate problems, severe problems, extreme problems). This part of the EQ-5D can be used to generate a health state index score, which is used to compute quality-adjusted life years for utilization in health economic analyses. The health state index score is calculated based on the responses to the 5 dimensions, providing a single value on a scale from less than 0 (where 0 is a health state

equivalent to death; negative values are valued as worse than death) to 1 (perfect health), with higher scores indicating better health utility. The second part of the questionnaire consists of a visual analog scale on which the patient rates their perceived health state from 0 (the worst health you can imagine) to 100 (the best health you can imagine). The EQ-5D-5L will be captured at Visit 2 and at 0 and 24 hours postdose of study drug.

Disability: Disability will be measured by determining the level of interference with normal activities with 4 response options including not at all; mild interference, marked interference; and need complete bed rest. This will be evaluated at 0 (pre dose), 0.5, 1, 2, and 24 hours postdose of study drug.

PGI-C: Patient global impression of change will be measured at 2 and 24 hours postdose of study drug with a 7-point scale ranging from very much better to very much worse.

Treatment Satisfaction: Treatment satisfaction will be evaluated at 48 hours postdose of the study drug by determining the patient's level of satisfaction (ranging from extremely dissatisfied to extremely satisfied); their willingness to take this treatment again (ranging from strongly disagree to strongly agree); if they would they recommend this treatment to another patient (ranging from strongly disagree to strongly agree) and their preference when comparing this treatment to the previous treatment ("prefer this treatment in comparison to my previous treatment" to "prefer my previous treatment in comparison to this treatment").

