- Sec. 5.6.3 (Details of Efficacy Analyses): In [Table LAIH. 5.3](#), ANCOVA was changed to ANOVA because ANOVA was the actual method for analyses.
- Sec. 5.6.3 (Details of Efficacy Analyses): Figures for ratio of achieving Pain Free, Pain Relief, and MBS-free, MBS-Free by Chosen Symptom up to 2 hours were added.
- Sec. 5.7.1 (Adverse Events): “AEs” were explicitly defined as “AEs are collected from Visit 1 to Visit 3.”
- Sec. 5.7.1 (Adverse Events): “Post-dose AEs” were defined as the same as the TEAE except without the restriction of the 48 hours cutoff after the dosing. In addition, its TFLs would be created.
- Sec. 5.7.1 (Adverse Events): “By PT by decreasing frequency with an incidence in any lasmiditan group $\geq 1.5\%$ and greater than placebo” was changed to “By PT by decreasing frequency with an incidence in any lasmiditan group $\geq 1.5\%$ and PT including “Vertigo.””
CCI
[REDACTED]
- Sec. 5.7.1 (Adverse Events): (AE): From “overview of AEs”, total number of events is deleted because it would not be used in CSR. “Pot-dose AEs” is added.
- Sec. 5.7.3 (Vital Signs and Weights): The wording “treatment emergent” was deleted because by nature, Vital Signs and weights were measured at Visit 3 which were beyond 48 hours from dosing, in general.
- Sec. 5.7.3 (Vital Signs and Weights): BMI was added.
- Sec. 5.7.4 (Laboratory Tests): The wording “treatment emergent” was deleted because by nature, lab tests were taken at Visit 3 which were beyond 48 hours from dosing, in general.
- Sec. 5.7.4 (Laboratory Tests): Both standard and conventional units’ outputs for continuous analysis were specified.
- Sec. 5.7.7 (Safety Topics of Interest): This section was newly added. **CCI**
[REDACTED]
- Sec. 5.8 (Subgroup Analysis): The analysis “Patients who fail the most recent triptan at any time before screening” was renamed as “Triptan responder vs. insufficient responder (based on the most recent triptan experience)” to clarify the definition (subgroup ID= SUB1).
- Sec. 5.8 (Subgroup Analysis): “Patients with one or more CVRF” was updated as “Patients with two or more CVRF” (subgroup ID= SUB12).
- Sec. 5.8 (Subgroup Analysis): New subgroup definitions and analyses were added. The entire subgroup analysis was summarized in [Table LAIH. 5.6](#).

- Sec. 5.8 (Subgroup Analysis): Analysis methods and statistical models were specified.

4. Study Objectives

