5.4. General Statistical Considerations

Statistical analysis of this study will be the responsibility of Lilly or its designee.

In general, we will use the following statistical methods unless otherwise specified. For detailed definitions of [T1] (primary objectives), [T2] and [T3] (2 key secondary objectives), see Section [5.6.1](#):

- For efficacy analyses based on proportion, the logistic regression used in [T1] will be applied. The model term includes treatment and baseline usage of preventive medications to reduce the frequency of migraine (Yes/No).
- When treatment group (PLA, LY50, LY100, LY200) is in a statistical model, it will be regarded as a categorical variable.
- For analysis based on continuous variable (change from baseline), if analysis of variance (ANOVA) is used then its covariate includes treatment and baseline usage of preventive medications to reduce the frequency of migraine (Yes/No). LSMeans will be used for estimation.
- For safety analyses and demographics, only descriptive statistics will be presented, and no statistical test will be conducted.
- Statistical tests will be conducted at a 2-sided significance level of 0.05. The 95% confidence interval will be presented if appropriate.
- No multiplicity adjustment for multiple tests (between the arms for the same efficacy objective, nor between the different objectives for the same arms) will be made except primary and two key secondary analyses ([T1], [T2], and [T3]).
- Analyses will be reported by 4 treatment groups (PLA, LY50, LY100, LY200) in general.
- Frequency tables such as those for AE or TEAEs will be sorted by LY_ALL, in decreasing frequency.
- For safety, 5 treatment groups (PLA, LY50, LY100, LY200, LY_ALL) will be displayed.
- For demographics, 6 treatment groups (PLA, LY50, LY100, LY200, LY_ALL, Overall) will be displayed. Here “Overall” means all combined arms (PLA + LY_ALL).
- For efficacy analyses based on proportions, odds ratio along with 95 % confidence interval will be calculated at 2 hours post-dose time point (each treatment vs. placebo).

- When Cochran-Mantel-Haenszel test is used for a multi-category response, baseline usage of preventive medications to reduce the frequency of migraine (Yes/No) is used for stratification (each treatment vs. placebo).

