- For Kaplan-Meier analysis, corresponding figures will be created. Quartiles and rates, along with 95% CIs, were estimated using the Kaplan-Meier method. Corresponding 95% CIs were estimated using the methods of Brookmeyer and Crowley, and Greenwood, respectively.
- When baseline usage of preventive medications to reduce the frequency of migraine (Yes/No) is included in a statistical model, it is based on CRF, not IWRs.
- Efficacy analyses are based on eDiary data, unless otherwise specified.
- Comorbid condition is based on Visit 1.
- When median is used for subgroup analysis (e.g. SUB4, body weight), the median is based on mITT population.

We will use the following analysis population rules unless otherwise specified (see population definitions in Section [5.3](#)):

- Protocol deviation summary will be based on all randomized and mITT/ITT.
- Demographics and Baseline characteristics will be based on mITT/ITT/safety population (SP).
- Efficacy analyses [T1], [T2], [T3], and MBS will be based on mITT/ITT/per-protocol set (PPS).
- Other efficacy and health outcome will be based on ITT.
- Safety analyses (e.g., AE, laboratory assessments/vital signs), medication, and treatment compliance/eDiary compliance will be based on SP.

When continuous variables, including change from baseline scores, is summarized using descriptive statistics, it will show n (number of subjects with available data), mean, median, standard deviation, minimum, and maximum.

Minimum and maximum values will be presented to the same precision as the raw data. Mean and median will be presented to one more decimal place than the raw data. Standard deviation will be presented to two more decimal places than the raw data. P-values will be presented to three decimal places.

Categorical variables will be summarized using counts and percentages. Unless otherwise specified, percentages will be calculated using the numbers of subjects in the summarized

population in each treatment group as denominators. Percentages will be presented with a precision of 1 digit after the decimal.

Observations collected prior to dosing will serve to determine a baseline measurement; the latest available measurement prior to dosing will be used as the baseline. For data collected by eDiary, the baseline values will be the Hour-0 assessment times identified in the eDiary.

SAS® software (version 9.2 or higher) will be used to perform most or all statistical analyses.

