If patients are pain free and are not experiencing any other migraine symptoms (i.e. nausea, photophobia, phonophobia, or vomiting), then they are total migraine free.

Modified Sustained Pain Free at 24 hours and 48 hours

Modified Sustained Pain-Free is defined as experiencing headache pain-free at two hours after the dose and no moderate or severe pain at the indicated assessment time, having not used any medications to treat migraine after the dose up to the assessment timing. Note that if a patient has missing evaluation at 24 hours, then he is excluded from the analysis instead of setting his response as nonresponder. The same is true at 48 hours evaluation.

Time to Meaningful Pain Relief Through 48 Hours

Meaningful Pain Relief timing is defined as the time when the corresponding eDiary question is answered as Yes.

Time to Pain Free Through 48 Hours

Pain Free timing is defined as the time when the corresponding eDiary question is answered as Yes.

Change from Baseline of EQ-5D-5L in Index Score

It is based on the EQ-5D Health Status Index Score. The Japan specific tariffs (Japanese population-based index value) for the EQ-5D Health Status Index Score is used. Change from baseline is based on Baseline (0 hour) and post-baseline (24 hours).

Change from Baseline of EQ-5D-5L in Visual Analog Scale

The change of EQ-5D-5L visual analog scale is based on Baseline (0 hour) and post-baseline (24 hours) from the onset of dosing.

HRQoL Measured by MQoLQ in 5 Domains

There are 5 domains in MQoLQ. Each domain will be analyzed separately: work functioning, social functioning, energy and vitality, feelings and concerns, and migraine symptoms. Each domain consists of 3 questions answered on a 7-point scale where 1 indicates maximum impairment and 7 indicating no impairment. A domain score is calculated by summing the responses to the 3 questions and the domain score ranges from 3 to 21. The response variable in this analysis is raw values at 24 hours.

Treatment Satisfaction

There are 4 questions. Each question will be analyzed separately. Distribution of responses and proportion of patients with agree or strongly agree will be summarized for each treatment group:

- the patient's level of satisfaction (ranging from extremely dissatisfied to extremely satisfied)
- their willingness to take this treatment again (ranging from strongly disagree to strongly agree)

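### The MQoLQ comparison (SAP ID 24) could be adjusted for the hour-0 EQ-5D-5L index at almost no cost; the planned analysis is unbiased, and any gain depends on a correlation the documents do not give

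*Protocol*

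**What the plan says.** **Endpoint.** Protocol Section 4 (Table LAIH.3) lists among the other secondary endpoints: "Mean HRQoL score for domains of social functioning, migraine symptoms, and feelings/concerns". SAP 5.6.3 analyses all five MQoLQ domains under ID 24.

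**Timing.** Protocol 9.1.2 schedules one administration: "The questionnaire will be administered 24 hours after the study drug". The diary grids (Protocol Appendix 5, SAP Appendix 1) show no pre-dose MQoLQ.

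**Analysis.** SAP 5.6.3 says of ID 24: "The response variable in this analysis is raw values at 24 hours". Table LAIH. 5.3 gives the method as ANOVA in the ITT population, and SAP 5.4 agrees on the population: "Other efficacy and health outcome will be based on ITT". On model terms, SAP 5.4 says: "if analysis of variance (ANOVA) is used then its covariate includes treatment and baseline usage of preventive medications". That bullet is written for continuous variables expressed as change from baseline, so applying it to a raw score is an inference. The SAP revision history shows that the label was considered: "ANCOVA was changed to ANOVA because ANOVA was the actual method for analyses".

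**What exists at hour 0.** Protocol 9.1.2 states: "The EQ-5D-5L will be captured at Visit 2 and at 0 and 24 hours postdose of study drug". Headache severity is also recorded pre-dose, as is the disability item: "This will be evaluated at 0 (pre dose), 0.5, 1, 2, and 24 hours postdose of study drug". SAP 5.6.3 already derives the hour-0 EQ-5D-5L index, with Japanese tariffs, for the change score in ID 22.

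**The concern.** Patients differ before dosing in how badly the attack affects them. If some of that difference persists in the 24-hour MQoLQ score, it stays in the residual variance of ID 24, because no hour-0 patient-reported value is in the model. The instrument covers the 24 hours after medication, so it has no baseline of its own. The hour-0 EQ-5D-5L index is a reasonable substitute: it covers usual activities, pain or discomfort, and anxiety or depression, which overlap in content with the MQoLQ domains.

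At stake is the width of the intervals for three doses against placebo on a listed secondary endpoint. Those intervals are widest for 50 mg, the smallest arm (81 planned). Neither bias nor type I error is in question.

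**Working it through.** **1. Is there a plan figure to reproduce?** Not for the MQoLQ: the documents give no SD, effect size or power for it. The stated power covers [T1] to [T3] only. A simulation of 200,000 runs used the planned arm sizes and the rates in Protocol 10.1.1, with Wald tests, a trend test with scores 0/50/100/200, and pain freedom independent of pain relief. It gives 95.2%, 95.0%, 92.2% and 86.9% overall, against the stated 93.6%, 94.9%, 91.2% and 85.6%. The arm sizes and rates are therefore read correctly, but this says nothing about ID 24.

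**2. Inputs.**
- Arm sizes: placebo 190, 50 mg 81, 100 mg 190, 200 mg 163 (Protocol 10.1.1). These are planned mITT counts. ID 24 uses ITT, so they only illustrate the scale.
- Test: two-sided 5% (SAP 5.4).
- SD of the domain score: set to 1.
- Correlation r between hour-0 EQ-5D-5L index and 24-hour domain score: **assumed**, 0 to 0.5.

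**3. Formulas.**
- Planned SE = sqrt(1/n1 + 1/n2). For 200 mg: sqrt(1/190 + 1/163) = 0.107 SD. For 100 mg: sqrt(1/190 + 1/190) = 0.103. For 50 mg: sqrt(1/190 + 1/81) = 0.133.
- With one baseline covariate in a linear model, the SE is multiplied by sqrt(1 − r²).
- Equivalent number of patients = 624/(1 − r²).
- For an effect with 80% power under the planned model, the standardised effect is 1.960 + 0.842 = 2.802. Adjusted power = Φ(2.802/sqrt(1 − r²) − 1.960). The effects concerned are 0.299 SD for 200 mg, 0.287 for 100 mg and 0.372 for 50 mg.

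Example, r = 0.3: 1 − 0.09 = 0.91; sqrt(0.91) = 0.954, so the interval is 4.6% narrower; 624/0.91 = 686; 2.802/0.954 − 1.960 = 0.977, so power is 83.6%.

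**4. Results.**

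| Assumed r | CI narrower by | Equivalent N (624 planned) | Power, if 80% unadjusted | SE, 200 mg | SE, 50 mg |
|---|---|---|---|---|---|
| 0 | 0% | 624 | 80.0% | 0.1068 | 0.1327 |
| 0.1 | 0.5% | 630 | 80.4% | 0.1062 | 0.1320 |
| 0.2 | 2.0% | 650 | 81.6% | 0.1046 | 0.1300 |
| 0.3 | 4.6% | 686 | 83.6% | 0.1018 | 0.1266 |
| 0.4 | 8.3% | 743 | 86.4% | 0.0978 | 0.1216 |
| 0.5 | 13.4% | 832 | 89.9% | 0.0925 | 0.1149 |

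The percentage narrowing does not depend on the arm sizes, so the mITT/ITT difference does not affect it.

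**5. Missing hour-0 values.** If a share m of patients lacked the covariate and was dropped, adjustment would help only when r² > m: r above 0.14 for m = 2%, above 0.22 for m = 5%. A rule that keeps those patients avoids this loss.

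**6. Cost when r = 0.** With 624 patients and five parameters (intercept, three treatment terms, preventive use) there are 619 residual degrees of freedom; the covariate leaves 618. The SE rises by about sqrt(619/618) − 1 = 0.08%.

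**The case against.** The case for leaving the plan alone is substantial.

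- **Nothing is wrong with the planned model.** Treatment plus preventive use is valid under randomisation, and a single post-dose MQoLQ fits what the instrument measures. A reader might infer that a baseline was wrongly omitted; none exists for this questionnaire. This stands.
- **The loss is not demonstrated.** A reader might infer that precision is certainly being given away. The documents contain no correlation, and two design features could keep it low. Condition [C2] in SAP 5.3 limits the analysis to moderate or severe baseline pain, which restricts the hour-0 range. Treatment, and rescue after 2 hours (Protocol 7.2.1.1), come between hour 0 and the 24-hour report. This stands, so the gain is stated only conditionally.
- **Not every patient supplies the covariate.** It is scheduled at hour 0 of a treated attack, and about 29% of randomised patients are expected not to dose. Among those who do, the entry can be missing. This stands, and the fix needs a missing-value rule.
- **Hour 0 may not always be pre-dose.** SAP 5.3 no longer requires the diary baseline to precede dosing, and the revision history says that patients who recorded it afterwards are now included in mITT. A value entered after dosing could carry a treatment effect. This stands, and a timing rule is needed.
- **Another hour-0 item could be chosen,** such as disability, headache severity or the EQ-5D-5L visual analogue scale. This is true. The index is preferred for its content overlap and because it is already derived for ID 22, but the documents do not settle the choice.
- **A common effect size across doses has no support.** Protocol 5.4 says 50 mg generally showed the least efficacy. The power column above is therefore tied to whatever effect has 80% power in each comparison and does not predict any dose's power.

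**Conclusion.** This is a cheap, optional improvement to a secondary analysis. ID 24 as planned estimates the treatment difference without bias and keeps its type I error. It does not use a related hour-0 value that the diary already collects. If that value correlates with the 24-hour score, intervals narrow by 0.5% to 13.4% for r from 0.1 to 0.5. The gain is small up to r = 0.3 (at most 4.6%) and becomes worthwhile from about 0.4.

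The result rests on an assumed r, a linear model, and a covariate that is truly pre-dose. Under those conditions the adjusted and unadjusted models target the same mean difference. A reader might infer that the secondary conclusions are underpowered because of this choice. The documents do not support that, since they set no power target for the MQoLQ. The endpoint also lies outside the [T1] to [T3] gatekeeping, so no confirmatory conclusion changes.

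A side benefit is clarity: the ID 24 model terms now have to be inferred from a bullet written for change scores.

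**What to change.** In SAP 5.6.3, ID 24:

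1. State the model for each domain: treatment (categorical), preventive use (Yes/No), and hour-0 EQ-5D-5L index (continuous).
2. Treat an hour-0 index recorded after the diary dosing time as missing for this purpose.
3. Set a missing covariate value to the mean over all arms combined, so that no ITT patient with a 24-hour score is dropped.
4. Keep the present model, without the index, as a supporting analysis.

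The cost is a few lines in the SAP, one model term and one degree of freedom; no new data are needed. The change should be fixed before unblinding. If made later, it should be labelled post hoc, with the present model kept as the main analysis.
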